6 STUDY SETTING

The study is a multicentre study and will be run within a number of UK NHS neuro oncology outpatient Trusts. The imaging analysis will be done remotely at the Walton Centre, Liverpool. The Trusts involved all have a neuro-oncology outpatient clinic where the patients will be approached and reviewed as part of the study. They also have appropriate MRI scanners attached to the trusts for the type of imaging sequences that are required. The local protocols for which MRI sequences are performed are slightly different in each trust which is why some patients may require an extra MRI scan.

The recruitment process is similar in each site however the location of the MRI scanners differs slightly. In sites where the MRI scanner is not on the same trust as the outpatient clinic, the costs of taxi journeys to the scanner and back will be covered.

7 SAMPLE AND RECRUITMENT

7.1 Eligibility Criteria

7.1.1 Inclusion criteria

- Patients aged \geq 65 years with a new diagnosis of GBM. Diagnosis made via histological confirmation following biopsy or debulking surgery or radiologically during an MDM meeting confirmed by a consultant neuro radiologist. This lower age limit is due to previous clinical trials which have established gold standard treatment regimes for patients under the age of 65. Patients aged 65 or over have less clinical trial data available to them and treatment decisions are more nuanced with a greater emphasis on quality of life given the poorer prognosis of older patients.
- Patients undergoing radiotherapy treatment to the brain for treatment of their GBM
- Patients able to undergo an MRI scan
- Patients undergoing treatment at one of the study centres
- Patient have capacity to participate in the study
- Patients with physical impairments that prevent them filling in their questionnaires involved in the study may still participate if they are able to communicate their answers through a third party

7.1.2 Exclusion criteria

- Patients not fit for radiotherapy treatment or having single agent chemotherapy with no radiotherapy
- Patients lacking capacity
- Patients who do not have sufficient grasp of the English language to be able to complete the questionnaires
- Patients unable to communicate their responses to the questionnaires
- Patients who are concurrently enrolled in a Clinical Trial of an Investigational Medicinal Product (CTIMP)

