1 BACKGROUND

Glioblastoma (GBM) is the commonest primary malignant brain tumour among the adult population with approximately 2,000 new cases diagnosed in the UK per year. Incidence peaks in the 7th and 8th decades of life and as our global population ages, rates are increasing. Outcomes from this disease remain poor with median life expectancy in the range of 12-18 months, dropping to 3-6 months in the older populationⁱ. The reasons for this are multifactorial, including more aggressive tumour biology in the older age group, decreased tolerance to treatment related side effects and the potential of under treatment by doctors within the older age group.

Given the poor prognosis in this group, treatment must be balanced against side effects and worsening quality of life. In patients aged 65 or over there is a lack of consensus on standard of care. Radiotherapy has a survival advantage over best supportive careⁱⁱ however the optimal dose of radiotherapy is yet to be established^{iiiiiv}. A recent Phase III trial randomised elderly GBM patients to standard radiotherapy with 60Gy in 30#, hypofractionated radiotherapy of 34Gy in 10# or temozolomide (TMZ) chemotherapy alone. For patients older than 65, survival was significantly longer with TMZ or hypofractionated radiotherapy than with standard radiotherapy^{vi}. Those with defects in the DNA repair protein MGMT did significantly better in the chemotherapy arm than those with intact MGMT, a result which was replicated in the NOA-08 trial which randomised elderly GBM patients to standard radiotherapy with 60Gy in 30# or TMZ alone. This non-inferiority trial showed TMZ to be a suitable monotherapy option, with greater effect seen in those with MGMT promoter methylation^{vii}. Recently published evidence has shown a survival benefit from adding concomitant and adjuvant TMZ to a hypofractionated radiotherapy regime of 40Gy in 15# in patients aged over 65, again with greater effect seen in those with MGMT promoter methylation^{viii}. There is therefore now evidence to support the use of concomitant chemoradiotherapy or chemotherapy or radiotherapy as single agents amongst elderly GBM patients and an increasing interest in using MGMT promoter methylation status as a biomarker. However there remains a paucity of data surrounding the clinical and radiological basis by which individual patients are assessed for treatment.

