Baseline clinical assessment of the patients will be conducted in the NHS neuro-oncology outpatient clinic setting. These will involve the EORTC-QLQ-C30 quality of life questionnaire with the BN-20 brain and ELD14 elderly patient subsets of questions added, the MOCA questionnaire (please see Appendix for examples of these questionnaires) and a record of the amount of corticosteroid the patient is currently taking. The EORTC-QLQ-C30 quality of life questionnaires are designed to be completed by the patient (they are allowed to ask for help completing from family/carer) and could therefore be taken home by the patient or completed in the waiting room rather than being completed within the clinic. There is a risk of the questionnaires not being filled in and posted back if participants forget. We have costed for stamped addressed envelopes to be given to the patients in order to post the questionnaires back. The study team (who know the participant and would usually speak to them on the phone anyway during their treatment pathway) are able to call the participant to remind them to post back the questionnaires. The MOCA is administered by a member of the study team.

The original copies of these questionnaires will be in the CRF, alongside details of the participant's age, gender, comorbidities, treatment plan and social situation which will be recorded by the study team.

In most cases, the participant will have undergone an MRI scan as part of their usual care plan prior to attending the neuro-oncology clinic. If this scan has the required imaging sequences needed for the BRITER protocol then no further scanning is required. This will be assessed by the neuro oncology consultant during the outpatient clinic appointment or a member of the study team prior to the appointment. A list of the required sequences will be readily available for the study team during this process. If not all of the required sequences were completed then the patient will undergo a further MRI scan. This will be done prior to the participant starting radiotherapy treatment but should not delay the start of their radiotherapy treatment. Depending on local guidelines, this scan will either take place on the same site or may require travel to another site. Travel costs will be covered for the patient and carer to attend the extra MRI scan.

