- 3D volumetric inversion recovery or MP-RAGE (additional sequence - to allow accurate quantification of cortical thickness/volumes using Freesurfer software in addition to scoring methods of atrophy, must be acquired at 1mm or below)
- Axial T2* gradient echo (4mm slice thickness)

The scan thickness and sequences performed may vary slightly between sites however prior to opening the sites will confirm they can produce the necessary sequences for [name] to produce 5 quantitative scores (tumour volume, contralateral hemispheric brain volume, contralateral cerebral hemisphere cortical thickness, microhaemorrhage score and white matter hyperintensity score) from the images which reflect the degree of potential vulnerability of the brain to the side effects of radiotherapy. These will then be analysed in relation to the clinical questionnaires, steroid usage and grade 3-5 CTCAE radiotherapy toxicity score using SPSS. Multivariable logistic regression models will be fitted to look for significant ($P<0.05$) relationships between the 10 point change in EORTC QLQ quality of life questionnaires and the MRI parameters. Exploratory statistical analysis of the relationships between the MRI parameters and the secondary endpoints will be performed although the study is not powered to detect statistically significant relationships between these.

The creation of the database and statistical analysis of the results will be performed by the CI with the help of a research assistant.

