7.2 Sampling

7.2.1 Size of sample

Sample size calculations have been performed assuming a clinically significant end point of a 10 point change (SD=22.1 taken from the EORTC website reference guide) in EORTC QLQ questionnaire score between baseline and 8 weeks. Estimated sample size for one-sample comparison of proportion to hypothesized value assuming a 2 sided alpha of 0.05 and power of 0.9 gives a sample of

73. However, allowing for 20% attrition in questionnaire completion, this results in a sample size of 91. With 73 patients at 8 weeks, we will have 90% power for 5% significance to detect 5% of patients achieving a 10 point change in QoL. However, this small a proportion will only allow us to fit one variable in the model. It has therefore been recommended by the statistical team to aim for a recruitment target of 100 patients in order to fit the 5 MRI variables to the model.

Patients who are enrolled within CTIMP studies will not be eligible to be recruited into the study as they would introduce too many unknown variables for adequate statistical analysis with a cohort of this size.

Previous work done by this study group has shown this is a feasible recruitment target over 2 years.

The study team will review recruitment at 9 months and if it has not reached 25% then they will explore ways to increase recruitment, including opening at other sites.

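### The primary model leaves out temozolomide although patients with and without it are enrolled, so an MRI association cannot be shown to be independent of chemotherapy

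*Combined protocol and SAP*

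**What the plan says.** Section 7.1.1 admits "Patients undergoing radiotherapy treatment to the brain for treatment of their GBM", with no condition on chemotherapy. Section 7.1.2 removes "Patients not fit for radiotherapy treatment or having single agent chemotherapy with no radiotherapy". Radiotherapy with TMZ is therefore eligible.

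The combination is not presented as unusual. Section 1 reports a survival benefit from "adding concomitant and adjuvant TMZ to a hypofractionated radiotherapy regime of 40Gy in 15# in patients aged over 65" and concludes: "There is therefore now evidence to support the use of concomitant chemoradiotherapy or chemotherapy or radiotherapy as single agents amongst elderly GBM patients".

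Section 5 lists among the CRF items "comorbidities, treatment plan and social situation which will be recorded by the study team". The same section defines the primary analysis as multivariable logistic regression looking for "relationships between the 10 point change in EORTC QLQ quality of life questionnaires and the MRI parameters". Section 7.2.1 justifies the target of 100 patients by the need to fit five MRI variables. No adjustment, stratification or sensitivity analysis for chemotherapy is described.

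Section 4.2 introduces the secondary outcomes, including grade 3-5 CTCAE toxicity, as ways of assessing the side effects of cranial radiotherapy. In section 5 the MRI scores are to be analysed against "clinical questionnaires, steroid usage and grade 3-5 CTCAE radiotherapy toxicity score using SPSS". Neither section says how an event in a patient on both treatments is attributed.

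**The concern.** The research question is whether MRI predicts side effects of cranial radiotherapy. Section 3 gives the intended use: to find patients who might do better with chemotherapy alone or supportive care. That use requires the radiotherapy effect to be distinguished from the effect of chemotherapy given with it.

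A QoL score cannot be split by treatment, and the model has no TMZ term. Any effect of TMZ on the 10-point change is therefore read as an effect of radiotherapy. If TMZ use also differs by MRI score, part of that effect moves into the MRI coefficients. As written, the analysis could not show whether this had happened, although the treatment plan is in the CRF.

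**Working it through.** **The plan's own figures.** The 73 in section 7.2.1 is for a one-sample proportion. The formula is n = [z(0.975)·√(p0(1−p0)) + z(0.90)·√(p1(1−p1))]² / (p1−p0)². With p0 = 0.05 and p1 = 0 it gives 72.99, so 73, although the plan does not state that pair. Attrition of 20% gives 73/0.8 = 91.25 (stated as 91). Neither figure allows for treatment. For what follows, 100 recruited less 20% leaves 80 evaluable.

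**Effect on a difference in rates.** The protocol gives no TMZ rates or effects, so every input here is assumed. The outcome rate on radiotherapy alone is 20% in low-vulnerability and 30% in high-vulnerability patients, a true difference of 10 percentage points. TMZ adds d points in both groups. The shares receiving TMZ are t_low and t_high.

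Observed difference = (30 + t_high·d) − (20 + t_low·d) = 10 + (t_high − t_low)·d

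| TMZ use, low/high | d = 5 | d = 15 | d = 25 |
|---|---|---|---|
| 70% / 30% | 31.5 − 23.5 = 8 | 34.5 − 30.5 = 4 | 37.5 − 37.5 = 0 |
| 50% / 50% | 32.5 − 22.5 = 10 | 37.5 − 27.5 = 10 | 42.5 − 32.5 = 10 |
| 30% / 70% | 33.5 − 21.5 = 12 | 40.5 − 24.5 = 16 | 47.5 − 27.5 = 20 |

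The split of TMZ use determines both the direction and whether there is any bias. At 70/30 the sign changes only if d exceeds 10/0.4 = 25 points.

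**Effect on a logistic model.** This was simulated with one standardised MRI score, 50% on TMZ and 40% with the outcome (all assumed). Only the direction in which TMZ use falls with vulnerability was simulated. The true MRI odds ratio (OR) is 2.0 per SD. Power is for 80 patients and one score, from 1,000 simulated trials per row.

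| TMZ odds per SD of vulnerability | TMZ outcome OR | MRI OR without TMZ term | Power without | Power with |
|---|---|---|---|---|
| divided by 2 | 2 | 1.77 | 65% | 76% |
| divided by 3 | 3 | 1.53 | 43% | 70% |
| divided by 3 | 5 | 1.34 | 25% | 71% |

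Adding TMZ restores an OR of about 2.0 in each row. With no link between TMZ and vulnerability, the unadjusted OR is 1.93 at a TMZ OR of 3. That small shift is the usual non-collapsibility of the odds ratio and not confounding. Across the 50 combinations run (2 true ORs × 5 selection strengths × 5 TMZ ORs), the unadjusted OR fell below 1 once: 0.95, at a true OR of 1.5 with both assumed factors at 5.

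**Cost of one more term.** At an assumed 40% outcome rate, 80 × 0.40 = 32 events. Events per variable go from 32/5 = 6.4 to 32/6 = 5.3. At the 5% proportion in section 7.2.1, 80 × 0.05 = 4 events, and the figures are 4/5 = 0.8 and 4/6 = 0.67.

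**The case against.** The strongest reply is that the mechanism for bias is assumed. The protocol does not link TMZ use to the MRI scores, and without such a link the bias is nil or small. This stands, and it makes the concern conditional. It does not remove it: section 1 refers to a clinical and radiological basis for assessing patients for treatment, so a link is not excluded, and the planned analysis would not reveal one.

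Several stronger readings are tempting, and the documents do not support them:
- *TMZ goes to fitter patients.* Nothing says so. The guide to chemotherapy that sections 1 and 3 name is a molecular marker.
- *Every grade 3-5 event in a TMZ patient counts as radiotherapy toxicity.* Section 5 calls the measure a radiotherapy toxicity score. The defect is a missing attribution rule.
- *The primary outcome is QoL loss.* Sections 4.2 and 5 define a 10-point change without direction.
- *The MRI relationship could be reversed.* That needs extreme inputs, as shown above.
- *The follow-up visits fall during adjuvant TMZ.* Section 1 gives no timing, so overlap is possible but not stated.
- *The CTIMP exclusion makes the omission inconsistent.* Section 7.2.1 excludes those patients because "they would introduce too many unknown variables for adequate statistical analysis with a cohort of this size". A recorded treatment plan is not an unknown variable, so the contrast is weak.

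It is also fair to say that the CTCAE analysis is exploratory and unpowered by the plan's own account, and that 80 evaluable patients cannot support a five-variable model in each treatment group. Both points stand. They limit the remedy to something modest and put its weight on the primary QoL model.

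**Conclusion.** The gap is real and limited. Both treatment groups are eligible, the treatment plan is recorded, and the stated model does not use it. A significant MRI association could not be claimed to be independent of TMZ, and a null result could not be cleared of masking by it.

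The size and direction of any bias are unknown. With an assumed TMZ effect of 15 percentage points, a true difference of 10 could appear as anything from 4 to 16 over the splits considered. The figures rest on assumed outcome rates, an assumed TMZ effect that is the same in both groups, and an assumed association between TMZ use and vulnerability. The design is not invalid, and eligibility is not at fault.

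**What to change.** In the analysis paragraph of section 5:
- Keep the five-score model as the primary analysis.
- Prespecify one sensitivity analysis that adds planned concomitant TMZ (yes/no), taken from the treatment plan recorded at baseline.
- Tabulate the five MRI scores and the QoL and CTCAE outcomes by TMZ group, descriptively, without separate five-variable models. The table of MRI scores will show whether TMZ use and vulnerability are linked.
- Record at the 4- and 8-week assessments whether adjuvant TMZ is being taken, for description only. It arises after baseline and may itself depend on toxicity, so it should not enter the model.
- Report haematological grade 3-5 events separately from the other CTCAE events.

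The cost is a yes/no item at each of the two follow-up visits, one further model and one table. Planned TMZ needs no new data collection provided the treatment-plan item captures chemotherapy. The drawback is one more term in a sparse model, so the adjusted estimate will be imprecise and should be reported with its confidence interval as a check on the primary result. Eligibility and treatment stay as they are.

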7.2 Sampling

7.2.1 Size of sample

Sample size calculations have been performed assuming a clinically significant end point of a 10 point change (SD=22.1 taken from the EORTC website reference guide) in EORTC QLQ questionnaire score between baseline and 8 weeks. Estimated sample size for one-sample comparison of proportion to hypothesized value assuming a 2 sided alpha of 0.05 and power of 0.9 gives a sample of

73. However, allowing for 20% attrition in questionnaire completion, this results in a sample size of 91. With 73 patients at 8 weeks, we will have 90% power for 5% significance to detect 5% of patients achieving a 10 point change in QoL. However, this small a proportion will only allow us to fit one variable in the model. It has therefore been recommended by the statistical team to aim for a recruitment target of 100 patients in order to fit the 5 MRI variables to the model.

Patients who are enrolled within CTIMP studies will not be eligible to be recruited into the study as they would introduce too many unknown variables for adequate statistical analysis with a cohort of this size.

Previous work done by this study group has shown this is a feasible recruitment target over 2 years.

The study team will review recruitment at 9 months and if it has not reached 25% then they will explore ways to increase recruitment, including opening at other sites.

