2 RATIONALE

The poor prognosis of older GBM patients leads to an emphasis on the need for focusing on quality of life when deciding on treatment regimes. We have pathological markers which can help us determine sensitivity of the tumour to chemotherapy however we have no such guidance when it comes to making decisions about radiotherapy. If we were able to predict the degree of side effects likely to be experienced by a patient from radiotherapy treatment then it would enable us to make more individually tailored, patient centred treatment plans.

We aim to see if analysis of pre-radiotherapy MRI scans including T2 gradient echo and susceptibility weighted imaging sequences can correlate with acute treatment related toxicity and quality of life amongst patients aged 65 or over undergoing partial brain radiotherapy for GBM. As these patients have an average life expectancy of 3-6 months within the UK we are focussing on acute rather than long term side effects of radiotherapy.

MRI sequences will be utilised to determine any markers of background subclinical microvascular or degenerative disease in the normal brain including microhaemorrhage secondary to hypertension or cerebral amyloid angiopathy and atrophy with cortical volume measurement of the contralateral hemisphere. Additional susceptibility weighted sequences will be performed to identify the presence of microhaemorrhages in the contralateral normal-appearing brain parenchyma. These will be semi-quantitatively assessed using a modified established microhaemorrhage scoring methodology. Absolute measures of the contralateral normal-appearing hemisphere cortical volumes will be acquired using FSL freesurfer software and a volumetric T1 weighted acquisition. These techniques will give us a number of quantitative scores that can then be assessed for correlation with changes in quality of life and toxicity scoring systems.

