4 RESEARCH QUESTION/AIM(S)

4.1 Objectives

The BRITER study is being performed in patients aged 65 or over who have a new diagnosis of GBM. It tests the hypothesis that there is a relationship between 5 scores of a 'vulnerable' brain seen on pre-treatment MRI and a clinically significant change in patient quality of life, as defined by a 10 point change in the EORTC QLQ questionnaire from baseline to 8 weeks post treatment.

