4.2 Outcome

The primary outcome is the proportion of patients with a 10 point change in the EORTC QLQ C30 quality of life questionnaire (with the BN-20 brain and ELD14 elderly patient subsets of questions added) from baseline to 8 weeks.

The impact of side effects from cranial radiotherapy will also be assessed by the secondary outcomes of

- MOCA cognitive screening questionnaire
- use of corticosteroids
- degree of grade 3-5 CTCAE toxicity
- overall and progression free survival

5 STUDY DESIGN and METHODS of DATA COLLECTION AND DATA ANALYSIS

The BRITER study is an observational cohort study. Eligible patients will be identified during the multidisciplinary team meeting by the participants' usual care team. They will have previously been informed of their diagnosis and then will meet a member of the oncology team to discuss treatment options. Once it has been decided with them by their usual care team that they are to have radiotherapy treatment, they will be given a PIS. After the patient has had sufficient time to read the PIS and have any questions answered by a member of the study team they will be asked to complete a consent form. They will also undergo the baseline clinical assessments prior to starting any

radiotherapy treatment. This will be done during the outpatient appointment with the neuro oncology team.

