The participant's treatment plan is not affected by enrolment in the study. The participant will then complete their radiotherapy treatment as planned. When they attend for their routine 4 week post-treatment follow up to the NHS neuro-oncology clinic they will repeat the EORTC-QLQ-C30 quality of life questionnaires and MOCA questionnaire as well as having assessment of their CTCAE radiotherapy toxicity score and steroid use. Again the EORTC-QLQ-C30 quality of life questionnaires could be sent to the patient in advance to complete prior to the clinic appointment or taken home and posted back. If the patient is unable to come to a clinic appointment during the required time frame they can be posted a questionnaire and send it back. The questionnaires should be completed within 3 to 5 weeks after treatment has finished. These will be recorded in the CRFs. Members of the study team are permitted to phone the patient to remind them to complete the questionnaires if they are not returned or can complete them over the phone with the patient. This would normally be done by the CNS or doctor who the patient will already know as part of their usual care team and would be accustomed to speaking to on the phone.

When participants attend for their routine 8 week (plus or minus 1 week) post-treatment follow up to the NHS neuro-oncology clinic they will repeat the same questionnaires and toxicity assessment. At this point their participation in the study is complete.

At the end of the study the results of the questionnaires from the CRFs will be transcribed into a database using Microsoft Excel. The CRFs will not contain the patient's name or recognisable patient details and the database will therefore be pseudo anonymised. A score of 24 or less on MOCA will be deemed abnormal. A change in baseline of 10 points or more on the EORTC-QLQ-C30 quality of life questionnaires will be deemed significant.

The MRI scans for the participants will be anonymised using the patient study ID and electronically transferred to [name], neuroradiologist The Walton Centre in Liverpool, for analysis. The following MRI sequences are ideally required:

- Axial T2 4mm slice thickness
- Volumetric T1 pre contrast (1mm or below)
- Post contrast volumetric T1 (1mm or below)
- DWI/ADC (4 mm slice thickness)
- Susceptibility weighted imaging (acquired volumetrically typically in the region of 1.5mm slice thickness but will vary with scanner setup)

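### The 73 patients relied on at 8 weeks rest on an unsourced 20% for questionnaire completion, with no stated allowance for death or loss of capacity despite the plan's own 3-6 month survival figure

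*Combined protocol and SAP*

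**What the plan says.** Section 7.2.1 obtains 73 patients from a one-sample comparison of a proportion and then inflates: "allowing for 20% attrition in questionnaire completion, this results in a sample size of 91". It relies on the uninflated number at the endpoint: "With 73 patients at 8 weeks, we will have 90% power for 5% significance". The target is then raised to 100, and the reason given is fitting five MRI variables, not mortality.

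Section 1 gives "median life expectancy in the range of 12-18 months, dropping to 3-6 months in the older" population. Section 2 applies the figure to the study group, as the reason for studying acute effects: "As these patients have an average life expectancy of 3-6 months within the UK".

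Section 4.1 measures the change "from baseline to 8 weeks post treatment", and Section 5 sets the visit: "When participants attend for their routine 8 week (plus or minus 1 week) post-treatment follow up". Baseline comes before treatment: "They will also undergo the baseline clinical assessments prior to starting any" radiotherapy.

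Section 7.3.2 withdraws participants who lose capacity and collects nothing further from them, while keeping what was already collected. Section 5 lists the safeguards against missing questionnaires: prepaid envelopes, completion by telephone, and study staff who "are able to call the participant to remind them to post back the questionnaires".

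**The concern.** The sample-size section and the background do not use the same picture of the cohort. The background justifies an acute endpoint by short survival. The sample-size section allows only for questionnaires that are not completed. The safeguards in Section 5 work against forgetting, and do nothing about death or lost capacity.

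Two things are at stake. First, the number of patients who supply an 8-week outcome, and with it the stated power, may be well below what the plan says. Second, no section says how a patient who dies or is withdrawn enters the logistic regression. By default the primary result would describe only patients who are alive, have capacity and respond, and the plan does not say so. If the MRI scores are related to early death or incapacity, the estimated association could be distorted.

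**Working it through.** **The plan's own figure.** 73 / (1 - 0.20) = 91.25. The plan prints 91 (strictly rounded up, 92), so the inflation reproduces. With the target of 100, the total loss that still leaves 73 is 100 - 73 = 27%.

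**Inputs from the plan.** 73 completers, 20% loss and 100 recruits (7.2.1); survival of 3-6 months (Sections 1 and 2); visit 8 weeks after treatment ends (4.1, 5); courses of 10, 15 and 30 fractions (cited in Section 1; the study fixes no schedule).

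**Assumptions.** Five fractions a week, so the courses last 2, 3 and 6 weeks and the visit falls 10, 11 or 14 weeks after radiotherapy starts. With 52.18/12 = 4.348 weeks per month, that is 2.30, 2.53 or 3.22 months. Time from baseline is longer. The 3-6 months is read as a median. Survival is S(t) = 0.5^((t/median)^k), where k = 1 is constant hazard and larger k is a hazard that rises with time. Loss of capacity is set to zero, because no rate is given.

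**Reading A: the 20% is non-response among survivors.** Completers = 100 x S(t) x 0.80. Reaching 73 requires S(t) of at least 73/80 = 91.25%.

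| k | Median (months) | 10 weeks | 11 weeks | 14 weeks |
|---|---|---|---|---|
| 1 | 3 | 47.0 | 44.6 | 38.0 |
| 1 | 6 | 61.3 | 59.7 | 55.2 |
| 2 | 3 | 53.2 | 48.9 | 36.0 |
| 2 | 6 | 72.3 | 70.7 | 65.5 |

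Example: k = 1, median 6, 10 weeks: 0.5^(2.30/6) = 0.767, and 80 x 0.767 = 61.3.

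Steeper hazards go higher. With a 6-month median at 10 weeks, k = 2.5 gives 75.1 and k = 3 gives 76.9. At the earliest permitted visit (7 weeks after a 2-week course), k = 2 gives 73.7.

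Section 2 says average where Section 1 says median. If 3-6 months is a mean under constant hazard, completers at 10 weeks are 80 x exp(-2.30/3) = 37.2 to 80 x exp(-2.30/6) = 54.5.

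**Reading B: the 20% is loss from every cause.** Completers = 100 x 0.80 = 80, above 73. The check is whether deaths fit inside 20%. Under constant hazard, deaths by 10 weeks are 1 - 0.767 = 23% (median 6) to 1 - 0.588 = 41% (median 3). The median that keeps deaths alone to 20% is t x (ln 2 / -ln 0.8)^(1/k) = t x 3.106^(1/k):

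| k | 10 weeks | 11 weeks | 14 weeks |
|---|---|---|---|
| 1 | 7.1 months | 7.9 | 10.0 |
| 2 | 4.1 months | 4.5 | 5.7 |

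At these medians nothing is left for incapacity or non-return.

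**What it means for the planned model.** The smallest odds ratio per SD of one MRI score detectable with 90% power at two-sided 5%, unadjusted, is about exp((1.960 + 1.282)/sqrt(N x p x (1 - p))). The event rate p is assumed.

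| N | p = 0.5 | p = 0.3 |
|---|---|---|
| 73 | 2.14 | 2.29 |
| 61 | 2.29 | 2.47 |
| 47 | 2.57 | 2.81 |

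**The case against.** The strongest reply is that a median does not fix early survival. A reader might infer that the plan's survival figure makes 73 unreachable, with about 72 of 100 as the most that could remain. The documents do not support that. The 72 belongs to one hazard shape (k = 2), a 6-month median and a 10-week interval; steeper shapes or an earlier visit within the window give 74-77. Without a shape assumption, the ceiling under reading A is 80. This stands, so no upper bound is claimed.

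It is also wrong to say that deaths were certainly left out. Attrition can be read as loss from any cause, and then 80 remain. What can be said is that no allowance for death or incapacity is stated. Even under constant hazard, a 6-month median leaves 76.7 alive at 10 weeks, enough for 73 if 73/76.7 = 95% of them have capacity and respond.

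Patients selected for radiotherapy, with unfit patients and those lacking capacity excluded (7.1), may live longer than 3-6 months. That is plausible and limits certainty. However, Section 2 applies the figure to these patients, and the plan gives no other. The lowest counts combine a 3-month median with the longest course, so they are an extreme case.

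Finally, 73 comes from a one-sample proportion calculation, not from the logistic regression. Falling below it is not a measure of lost power for the study's hypothesis. That also stands: 73 serves here only as the plan's own benchmark.

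**Conclusion.** The point holds in a limited form. The plan relies on 73 completers and 90% power but does not support them against its own survival figure. Reading A needs at least 91% survival to the visit. Constant hazard with a 3-6 month median gives about 47-61 of 100 at 10 weeks and 38-55 at 14 weeks. A strongly rising hazard with a 6-month median gives about 72-77 at 10 weeks. Reading B leaves 80 only if deaths, incapacity and non-return together stay within 20%, which at 10 weeks needs a median of at least 7.1 months (constant hazard) or 4.1 months (k = 2) for deaths alone. Reaching 73 is possible, but it depends on favourable values of median survival, hazard shape, course length and response, none of which the plan states.

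These figures rest on five fractions a week, the courses cited in Section 1, survival counted from the start of radiotherapy, and no loss of capacity. A reader might also infer that the primary result will be biased in a known direction. The documents give no relation between the MRI scores and death or incapacity, so neither direction nor size can be stated. This should be corrected; confidence is medium.

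**What to change.** **(a) Section 7.2.1.** Replace the single 20% with separate expected losses by the end of the 8-week window: deaths, capacity withdrawals and unreturned questionnaires. Give each a source or a stated range, and give the resulting number of completers. The team's retrospective work mentioned in 7.2.2 is a possible source if it recorded survival. Restate power or precision at that number for the planned logistic regression. The recruitment target need not rise.

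**(b) Section 5, analysis.** State that the primary result applies to patients alive, with capacity and responding at 8 weeks. Add one prespecified sensitivity analysis that counts death or capacity withdrawal before the end of the window as deterioration. It should not replace the primary analysis, because it mixes tumour death with loss of quality of life. It also presupposes that the direction of the 10 point change has been defined, which is a separate matter. Tabulate the five MRI scores by completer, died, withdrawn and not returned.

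**Cost.** No new data are needed: survival is collected at the end of the study (8.6), and data obtained before a capacity withdrawal are kept and used (7.3.2). The change needs a protocol amendment, which the sponsor classifies as substantial or not (8.2), and a little more analysis. The stated number of completers will probably be less favourable.
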